Study Procedures		Visit 1 Screening (Day -45 to 0)	Visit 2 Treatment #1 (Day 0)	Visit 3 Follow-Up #1 PI Assessment (Day 30)	Visit 4 Treatment #2 (Day 45)	Visit 5 Follow-Up #2 Tx2 1M (Day 75)	Visit 6 Follow-Up #3 Tx2 3M (Day 135)
Demographic & Eligibility	Informed Consent ; Eligibility Criteria Medical History & Demographics	X					
Safety Assessments	Adverse Events; Concomitant Medications		X	X*	X	X	X
Study Intervention	BBL /MOXI/ Halo		X		X		
Assessments	Standard Photography; VISIA Imaging/Analysis	X				X	X
Evaluations	Global Aesthetic Improvement Scale						X

*Visit 3 determine whether patient is candidate for second treatment.

Study Visits

Pre-Study Procedures

Prior to the start of the study, potential subjects will be screened for eligibility requirements via chart review on EPIC. Prospective subjects will be informed of study details and study visit instructions as detailed in section 6. An appointment to visit the clinic for an official screening visit will be scheduled if interest is demonstrated. Additionally, if subjects express an interest in the procedure during a clinic appointment with [name], he may discuss the study with them and assess the treatment area. If a subject is deemed a good candidate, they will be connected to a research coordinator to answer any further questions and provide consent.

Visit 1: Screening (Day -45 to 0)

The purpose of the study, eligibility criteria and potential risks will be discussed with the potential subject. All interested candidates will be given an IRB approved Informed Consent Form (ICF) as detailed in section 5.2, with adequate time for review. The Investigator and/or designee will address questions and/or concerns raised by the subject. Those subjects who elect to participate will sign the consent form prior to any study procedures. The subject will receive a signed copy of their ICF and the original will be kept in the study file. Subjects will then be screened to ensure they meet all study criteria. The following is a complete list of the screening and enrollment activities to be performed:

1. Obtain informed consent and HIPAA authorization.
2. Assign a screening number to candidate subjects that sign the initial paperwork.
3. Collect a brief medical history including current medications, skin type, allergies, major conditions, or illnesses, etc. and assess if subjects meet eligibility criteria.

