4. For those that pass eligibility requirements and are females of childbearing potential, perform a urine pregnancy test. If the test is negative or candidate is male, the subject will be enrolled in the study and assigned a subject number.
5. Obtain close up and standard photography as described in section 8.1.
6. Obtain photographs and measurements using the Vectra H2 3D Imaging System and VISIA Imaging System as described in section 8.1.

This visit will take 30-45 minutes.

Treatment(s): Visit 2 (First treatment), Visit 4 (Second treatment* - if indicated, see Visit 3)

A member of the study team will record concomitant medications and will ask subjects if they have experienced any changes in their health since the previous visit. If an adverse event (AE) is reported then the Investigator will be informed, and an AE log will be completed/updated for PI review.

The following activities will be completed before the treatment:

1. Subjects will be asked to wash off all skincare products at least 30 minutes prior to each scheduled clinic visit using a cleanser of your choice. No other topical products should be applied to the treatment area until the study visit has been completed. If a subject arrives having not removed skincare products, she or he will be required to remove the residual product at the clinic and wait at least 20 minutes prior to procedures.
2. Subjects will acclimate to ambient temperature and humidity conditions for 15 minutes prior to any procedures being done.
3. A trained staff member will apply a topical triple anesthetic (benzocaine, lidocaine, tetracaine) to anesthetize the areas being treated. After allowing 30 minutes for the anesthetic to take effect, the skin will be cleansed and prepped with antiseptic.

The procedure will then be performed in our Plastic Surgery clinic following standard of care procedures. A trained staff member will treat the subject's face with BBL/MOXI/HALO. Treatment settings and parameters will be determined by the provider and will be chosen according to Fitzpatrick skin type and location of the body for which it will be used. Ultimately, 4-6 passes will be performed at the discretion of the provider.—Post-treatment cooling will be offered at the discretion of the treating provider and depending on clinical availability.

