After the procedure, subjects will be provided appropriate post-treatment care instructions as deemed appropriate by the Investigator or study staff. Subjects will be instructed that blistering, bleeding, oozing, strong pain, swelling persisting for more than 72 hours, or signs of infection (e.g., pus, drainage, fever) are cause for immediate concern and they should contact the investigator and/or his designee, to be evaluated. Expected downtime after BBL/MOXI/HALO is expected to be 7-10 days.

The treatment visit(s) is expected to take approximately 1 hour.

*A subset of subjects will return for a second treatment 45-60 days after the initial treatment. The PI and/or Sponsor will make a determination if a second treatment would be beneficial to the subject. All follow up visits will be scheduled accordingly.

PI Assessment: Visit 3 (1-month follow-up from initial treatment)

The physician will assess the patient at their 1-month follow-up after the initial treatment. The treating physician will determine if a single treatment is sufficient for achieving aesthetic goals or a second treatment is indicated based on the patient's presentation. Candidacy for a second treatment may involve assessment of the following factors:

- Stage of healing
- Absence of complications and adverse events
- Treatment tolerance by patient
- Patient interest and consent
- Review of VISIA data and Photography

Follow Up Visits (1M & 3M post final treatment): Visit 3 & 4 (Single tx) or Visit 5 & 6 (Double tx)

At a minimum, all subjects will return for follow-up visits at 1 month (\pm 7 days) and 3 months (\pm 7 days) after the final treatment.

The following activities will be performed on all study subjects during the follow-up visits:

1. The physician or study staff will ask subjects if they have experienced any changes in their health since the previous visit. Changes will be recorded accordingly. If an adverse event (AE) is reported then the Investigator will be informed, and an AE form will be completed.
2. Subjects will acclimate to ambient temperature and humidity conditions for 15 minutes prior to any procedures being done.
3. The physician or study staff will perform an examination of the skin in the treatment area
4. Obtain post-treatment close-range and standard photography as described in section entitled, "Assessments", for research purposes.

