5. Obtain post-treatment photographs and measurements using the Vectra H2 3D Imaging System and VISIA Imaging System as described in section entitled, "Assessments", for research purposes.

These visits will take about 30 minutes.

Assessments

Photography Procedures

NIKON D7200

Standard and close-range of the face will be utilized for evaluation of pigmentation. These photographs will be taken utilizing the Nikon D7200 at Baseline (Screening Visit), 1-month post-treatment and 3-months post-treatment.

VISIA CR Imaging System

Subjects will be instructed to adopt neutral, non-smiling expressions for each photograph. Images will be taken of each applicable subject with diffuse pigmentation of the face using the Vectra H2 3D Imaging System at Baseline, 1-month post-treatment and 3-months post-treatment. Each subject will have a total of 3 photos taken (right side, left side and center view).

Potential Risks

Risks of Anesthetic

Allergic Reaction (Rare)

There is a possibility of an allergic or toxic reaction to anesthesia used to numb the areas. Subjects will be questioned with regard to any history of allergies and carefully monitored for signs of allergic reaction.

Risks of Treatments

BBL: Broad Band Light

Erythema: (Occasionally < 3%)

May develop within the irradiated areas but are usually temporary and fade within 24-72 hours. There is a 90% chance of transient edema and 99% chance of erythema to occur after treatment.

Swelling and/or itching: (Occasional <3%)

May occur in the area of treatment and may last up to several hours. The pattern of the treatment may be visible on the skin, but this usually fades with healing. Itching and hive-like appearance may also occur.

Bruising: (Rare < 1%)

A mild bruising may occur at the treatment area as a result of laser exposure. This is usually transient and resolves in a few hours to few days.

Skin roughness and/or peeling (Occasional <3%)

Patients can expect their treated skin to feel rough like sandpaper for a few days while the skin heals. This is transient and should resolve in a few days.

Lasers: MOXI (Non-ablative Laser Facial Resurfacing & HALO (Fractionated Laser)

Blistering, burning, scaling and infection: Rare < 1%)

A crust, blister or superficial wound can occur at the treatment area. The risk of infection will be minimized by proper wound care.

Bruising: (Rare < 1%)

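### The 15-minute acclimation required before follow-up VISIA imaging is missing from the baseline visit, and the product-removal rule is not tied to any imaging session

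*Combined protocol and SAP*

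**What the plan says.** **Baseline.** Both visit schedules place the baseline VISIA image at Visit 1. Under Study Visits, Visit 1: Screening, the activities are introduced by "The following is a complete list of the screening and enrollment activities to be performed". The six items are consent, a screening number, history and eligibility, a pregnancy test where relevant, photography, and finally "Obtain photographs and measurements using the Vectra H2 3D Imaging System and VISIA Imaging System as described in section 8.1". The section ends: "This visit will take 30-45 minutes".

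**Follow-up (1 and 3 months after the final treatment).** Item 2 reads "Subjects will acclimate to ambient temperature and humidity conditions for 15 minutes prior to any procedures being done". Photography is item 4, and item 5 begins "Obtain post-treatment photographs and measurements using the Vectra H2 3D Imaging System and VISIA Imaging System". The list has no item on removing skincare products.

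**Treatment visits.** The list of activities before treatment contains the same acclimation sentence. It is also the only place where product removal appears: "Subjects will be asked to wash off all skincare products at least 30 minutes prior to each scheduled clinic visit". A subject who arrives with product on is covered by "she or he will be required to remove the residual product at the clinic and wait at least 20 minutes prior to procedures". Neither schedule marks VISIA imaging at a treatment visit.

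**Assessments, Photography Procedures.** This section specifies facial expression, three views and time points. It says nothing about the state of the skin.

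**Analysis.** Project Summary describes a non-controlled study. Statistical Analysis defines the primary effectiveness outcome as a paired comparison of baseline with the post-baseline VISIA results.

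**The concern.** In a single-arm before-and-after comparison, the baseline image does the work of a control. Anything that differs between the baseline session and the later sessions, other than treatment and time, enters the estimate of effect, and no concurrent group can remove it. The VISIA parameters listed under Primary Endpoints include red areas, spots, pores, UV spots and porphyrins. By requiring acclimation before follow-up procedures, the protocol itself treats skin state as something to control, but it does not ask for the same step before the image against which every later image is judged. Because no completion record is called for, an analyst could not tell afterwards which baseline images were taken on acclimated, product-free skin. A baseline image cannot be retaken once the subject has been treated.

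**Working it through.** The plan gives no figure for this issue, so there is nothing to reproduce. The check is a comparison of the visit lists, followed by two illustrations on assumed values.

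**1. Written preparation by session**

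| Session | VISIA image scheduled | 15-minute acclimation listed | Product removal listed |
|---|---|---|---|
| Visit 1 (baseline) | Yes, last of six items | No | No |
| Treatment visits | No | Yes | Yes, with arrival check and 20-minute wait |
| Follow-up, 1 and 3 months | Yes, item 5 | Yes, item 2 | No |

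Between the two rows that are compared in the analysis, the lists differ on acclimation and agree on product removal. The removal sentence refers to each scheduled visit, so its wording reaches baseline and follow-up alike. Its enforcement step is written only where no VISIA image is taken.

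**2. If product removal is equally loose at both sessions, percent change is not distorted**

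Let r be the true reduction and m the share of features hidden by product at both sessions. The reported reduction is 1 − (1 − r)(1 − m)/(1 − m) = r. A true 20% reduction is still reported as 20%. Distortion from product requires a difference between sessions, which the documents do not show.

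**3. Acclimation: effect on the plan's percent change**

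The plan's formula is (visit mean − baseline mean) × 100 / baseline mean. Suppose there is no true effect and the unacclimated baseline reads (1 + k) times its acclimated value. The reported change is then 1/(1 + k) − 1. The values of k are assumptions:

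- k = +0.05: 1/1.05 − 1 = −4.8%
- k = +0.20: 1/1.20 − 1 = −16.7%
- k = −0.05: 1/0.95 − 1 = +5.3%
- k = −0.20: 1/0.80 − 1 = +25.0%

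The sign depends on whether skin reads high or low on arrival, which the documents do not say and which may differ by parameter.

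**4. Acclimation: effect on the paired test**

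Inputs: n up to 15 (Project Summary) and alpha 0.05 (Statistical Analysis; two-sided is assumed because sidedness is not stated). Let b be an assumed mean shift in SDs of the paired difference, with zero true effect. The rejection probability comes from the noncentral t distribution with n − 1 degrees of freedom and noncentrality b√n. For b = 0.25 and n = 15 the noncentrality is 0.25 × √15 = 0.97.

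| b | n = 15 | n = 10 |
|---|---|---|
| 0 | 0.050 | 0.050 |
| 0.1 | 0.065 | 0.059 |
| 0.25 | 0.147 | 0.109 |
| 0.5 | 0.438 | 0.293 |

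These rates are per comparison and require a shift in the mean. Arrival states that vary between subjects and average out would add noise, not bias.

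**The case against.** The strongest reply is that the gap may be small in practice. Baseline imaging comes last in a visit of 30 to 45 minutes, after consent, history, eligibility and any pregnancy test. Many subjects could have been indoors for about 15 minutes by then. The follow-up visit fits acclimation, examination and imaging into about 30 minutes, so the length of Visit 1 does not show that there was no time. This stands as a reason to expect a modest effect. It does not close the gap, because the interval is neither required nor recorded at baseline.

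A reader might also draw three stronger conclusions, which the documents do not support.

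- *That baseline skin carries product and follow-up skin does not.* The removal rule is worded for every scheduled visit, and neither imaging list repeats it. Pre-Study Procedures also says that visit instructions are given before the screening appointment. The rule is misplaced, but no baseline-to-follow-up difference is shown, so figures that assume product hides features at baseline only do not follow.
- *That every subject's result is shifted systematically.* Arrival state varies by person and day, and no document gives a size or direction.
- *That all efficacy evidence depends on this contrast.* The clinician's Global Aesthetic Improvement Scale is also listed under Primary Endpoints. The planned comparisons among post-treatment visits, such as 1 against 3 months, share the same written preparation.

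**Conclusion.** The point holds in a limited form. One step, the 15-minute acclimation, is required before follow-up images and is absent from a baseline list that calls itself complete. The product-removal rule and its arrival check are not attached to any imaging session, and the imaging section sets no skin preparation. Any difference in preparation that results is confounded with treatment in the primary paired comparison. The amount of bias is unknown: the percentages and rejection rates above rest on assumed shifts and show only that a moderate mean shift would matter with 15 subjects. The conclusion assumes that sites follow the lists as written; if staff already acclimate subjects at Visit 1, what remains is an undocumented step.

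**What to change.** Move the existing product-removal rule, the arrival check with its 20-minute wait, and the 15-minute acclimation into the VISIA and photography procedure under Assessments. State that they apply before every image set: Visit 1 (in-clinic steps after consent) and each 1-month and 3-month visit. Add them to the Visit 1 and follow-up lists, and keep a cross-reference in the treatment-visit list so that nothing changes there. Record completion of each step on the imaging form. For subjects already imaged without this preparation and not yet treated, repeat the baseline image under it.

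The cost is protocol wording, tick-boxes on a form and a few minutes more at Visit 1, since acclimation can run alongside consent and history. Up to about 20 minutes more is needed only when product has to be removed in the clinic. No new equipment or staff is required.

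### The only pregnancy test is at screening, up to 45 days before treatment 1 and up to 90 days before a Day 45 treatment 2, and nothing repeats it before either treatment

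*Combined protocol and SAP*

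**What the plan says.** Step 4 of the screening visit reads: "For those that pass eligibility requirements and are females of childbearing potential, perform a urine pregnancy test". A negative result leads to enrollment. Inclusion criterion 5.1 also mentions a pregnancy test, placed before the screening visit. Whether or not that is the same test, it is no later than screening. Criterion 5.2 requires contraception. Exclusion 13 bars women who are pregnant or plan to become so during the study, and exclusion 12 bars a list of medications. Both schedule tables mark eligibility at Visit 1 only.

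At the treatment visits (Visits 2 and 4) the plan says: "A member of the study team will record concomitant medications and will ask subjects if they have experienced any changes in their health". The one stated follow-on action is: "If an adverse event (AE) is reported then the Investigator will be informed, and an AE log will be completed/updated for PI review". Three preparatory steps come next: removal of skincare products, acclimation ("Subjects will acclimate to ambient temperature and humidity conditions for 15 minutes prior to any procedures being done") and topical anesthetic. Treatment then follows.

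For subjects considered for a second treatment, the footnote to the dual schedule says: "Visit 3 determine whether patient is candidate for second treatment". The Visit 3 section adds: "Candidacy for a second treatment may involve assessment of the following factors". Its five factors name neither pregnancy nor medication.

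**The concern.** An exclusion that can come to apply after enrollment protects a subject only if someone looks again before treatment. Pregnancy is such an exclusion, and a screening test cannot detect a pregnancy that begins after it. The question about health changes can bring out a pregnancy the woman knows of, but not one she is unaware of. Even for a known pregnancy, the text sends only a reported adverse event to the Investigator and does not say that treatment is withheld.

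The same gap exists, in a narrower form, for medications. They are recorded at each treatment visit, but no text compares the record with exclusion 12. This also touches the primary endpoint. Several of the listed drugs act on pigmentation or skin aging, the baseline VISIA images are taken at Visit 1, and there is no control group. The effect of a drug started after baseline could not be told apart from the effect of treatment.

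**Working it through.** The plan states no figure for the age of the test, so there is none to reproduce. The check is date arithmetic and a reading of what happens between the test and each treatment.

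**Inputs**
- Screening, and so the test: Day -45 to Day 0 (both schedules; Visit 1 heading).
- Treatment 1: Day 0.
- Treatment 2: nominal Day 45 (Dual Treatment Arm schedule); 4-8 weeks, or 28-56 days, after treatment 1 (Project Summary); 45-60 days after treatment 1 (footnote to the treatment visits).

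**Formula:** age of test = treatment day minus screening day.

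| Treatment | Shortest | Longest |
|---|---|---|
| Treatment 1 | 0 - 0 = 0 days | 0 - (-45) = 45 days |
| Treatment 2, Day 45 | 45 - 0 = 45 days | 45 - (-45) = 90 days |
| Treatment 2, 4-8 weeks | 28 - 0 = 28 days | 56 - (-45) = 101 days |
| Treatment 2, 45-60 days | 45 - 0 = 45 days | 60 - (-45) = 105 days |

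The test can be same-day at treatment 1. At treatment 2 it is never less than 28 days old.

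**What stands between the test and treatment**
- *Pregnancy:* required contraception, which lowers the risk but detects nothing, and the health question, which finds only what the subject knows.
- *Medication:* the Visit 3 safety record carries the footnote on second-treatment candidacy, so a drug started by Day 30 has a route to the physician. Two periods remain: screening to Day 0, and Visit 3 to treatment 2. The second lasts 45 - 30 = 15 days at Day 45, 56 - 30 = 26 days at Day 56, and 60 - 30 = 30 days at Day 60.

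**Rough likelihood.** The documents give no rates, so every input except the maximum of 15 subjects is an assumption: 5 to 15 women of childbearing potential, 1% to 10% pregnancies per year on contraception, and 28 to 42 days during which a pregnancy goes unrecognized. Expected unrecognized pregnancies at one treatment = women x yearly rate x days / 365.
- Low: 5 x 0.01 x 28 / 365 = 0.004
- Middle: 10 x 0.05 x 28 / 365 = 0.04
- High: 15 x 0.10 x 42 / 365 = 0.17

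The high case needs all 15 subjects to be women of childbearing potential, although the trial admits men and women aged 20-75. Where the test is more recent than the assumed unrecognized period, the number is smaller; it is zero for a same-day test at treatment 1.

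**The case against.** The strongest reply is that the remaining risk is small. The plan treats this as a non-significant risk device and says the treatments are already standard of care in the clinic, alone or combined. Contraception is mandatory, women planning pregnancy are excluded, and staff ask about health at every treatment visit. The documents give no harm to pregnancy from these devices. Standard-of-care procedures at the clinic might include a test, and the visit-outline figure and consent pages are not available. All of this limits how serious the point is. It does not supply a check: none of the visible text calls for a test, an eligibility review or a withheld treatment.

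A reader might also infer more than the documents support.

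- *That a lightening drug used at any time after screening breaches the 4-month washout at both treatments.* Use that begins after Day 0 cannot affect treatment 1. The plan also gives no date from which washouts are counted, and eligibility is marked at Visit 1 only, so they may be entry criteria.
- *That up to 0.43 women could be treated with an unrecognized pregnancy.* That figure (15 x 0.10 x 105 / 365) counts every conception between the earliest screening and the latest second treatment, including pregnancies a woman would know of and could report.
- *That a full set of deferral rules by washout length is needed.* Antiplatelet and anticoagulant drugs have no washout in exclusion 12, so such rules would give nothing workable for them. The Investigator's judgment is the better tool.
- *That missing Visit 3 imaging is part of this point.* The candidacy factors include "Review of VISIA data and Photography", while the dual schedule marks no imaging at that visit. That is a separate inconsistency, and nothing here depends on it.

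It is also fair to say that other exclusions, such as suntan or immunosuppressive drugs, can change after screening. The fix stays with exclusions 12 and 13, for which the needed information is already collected or costs one strip.

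**Conclusion.** The point holds as a modest safety gap. The test ages follow directly from the plan's own visit windows and need no assumption. That no check precedes either treatment rests on the visible text. The consequence is that the plan, followed to the letter, permits treatment of a woman whom exclusion 13 bars, provided she does not know she is pregnant. On the assumed inputs the expected number at any one treatment is well below one (0.004 to 0.17), and the size of any harm cannot be judged from the documents. A reading that the trial is unsafe, or that subjects are not questioned at all before treatment, goes beyond the text. The case for change is that the plan set these exclusions itself and can confirm them on the day at little cost. The medication part is the weaker of the two and applies to the two periods identified above.

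**What to change.** Amend both schedules and the treatment-visit text as follows.

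1. For women of childbearing potential, do a urine pregnancy test at Visit 2 and again at Visit 4, during the 15-minute acclimation and before the anesthetic. The Visit 1 test counts for Visit 2 if both fall on the same day. Withhold treatment if the result is positive.
2. At the same two visits, have the staff member who already records medications and health changes check them against exclusions 12 and 13 and refer any hit to the Investigator, who decides before treatment whether to defer or omit it.

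The age of the pregnancy test then becomes 0 days at both treatments. The cost is a small amendment, at most 15 subjects x 2 visits = 30 urine strips, a few minutes per treatment visit, Investigator time only when there is a hit, and an occasional deferred or omitted treatment. No extra staff or visits are needed for the checks themselves.
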